7.4.3 Method for Assigning Subject to Treatment Groups

The statistician involved in this study will develop the programs necessary for the random number generator to create the randomization. Investigational Drug Services (IDS) will be performing randomization via REDCap to ensure proper blinding of the study team. They will also be responsible for distributing the study medications according to assigned group as per their standard operating procedure.

7.4.4 Subject Compliance Monitoring

For norethindrone, low and high dose CBD, the study team will be dispensing study medications. Adherence will be assessed daily via diary entries. Compliance monitoring will be done for all arms. These email are automatically generated via the Redcap system. It will be further verified at monthly visits using pill counts and/or visual inspection of liquid containing bottles as indicated.

7.4.5 Blinding of the Test Article

The norethindrone provided will be in individual identical packets. All study participants will be receiving norethindrone as standard of care treatment for endometriosis and this drug will not be blinded. The placebo, low and high dose CBD will be provided in identical vials. CBD Concentration will be adjusted so that subjects are each receiving equal volume of drug. In addition, CBD oil is usually blended with a carrier oil, such as coconut oil or hemp seed oil. The placebo drug consists of the same carrier oil.

The drug will be kept and dispensed in the Investigational Pharmacy at Penn State Hershey Medical Center and they will hold the randomization and unblinding key as needed. Investigational Drug Services will be responsible for blinding the test drug to the investigators and to the participants.

7.4.6 Receiving, Storage, Dispensing and Return

7.4.6.1 Receipt of Test Article

The study drug (CBD) will be obtained from an online source (Nuleaf Naturals). Testing to ensure quality up to the FDA standards of an oromucosally (sublingual)-administered drug product intended for use as a drug in a patient population have been performed. This testing was done by Keystone laboratories located in Harrisburg, PA.

The placebo (hemp seed oil) will also be obtained from an online source (Organic Infusions) and has been subjected to the same testing as described above.

The norethindrone will be purchased through a pharmacy wholesaler from a manufacturer. The manufacturer, lot information, and expiration for the product used in the study will be documented by the IDS pharmacy.

The norethindrone, hemp seed oil (placebo), cannabidiol products (study drug) will be monitored, held, packaged, and dispensed by our Investigational Drug Services (IDS) Pharmacy. IDS will be responsible for randomization.

Oxycodone will be provided as a rescue pain medication if requested by the participant AND determined to be medically necessary. An oxycodone prescription will be provided to the participant's pharmacy of choice. Oxycodone use will be monitored by self-report in the daily electronic diaries.

7.4.6.2 Storage

The drug will be stored with the Investigational Drug Services Pharmacy at Penn State Health. They will monitor the drug's stability and will assume appropriate storage conditions per institutional policy.

7.4.6.3 Preparation and Dispensing

Investigational Drug Services Pharmacy at Penn State Health will be responsible for packaging and dispensing the study drug per protocol and institutional policy.

IDS will prepare and dispense the 20mg sublingual CBD used for the pharmacokinetic portion of the study.

7.4.6.4 Return or Destruction of the Test Article

We will be requiring the return of all unused study drug, placebo and norethindrone medications at the conclusion of the study. There will be no study drug to return or destroy at the end of the pharmacokinetic portion of the study.

7.4.6.5 Prior and Concomitant Therapy

See Section 7.2.1 Prescreen

8.0 Subject Numbers and Statistical Plan

8.1 Number of Subjects

We plan to enroll and randomized 36 participants. Page 25 of 37 (v.01/21/2019) We would anticipate a 50% screen failure rate. There are multiple on-going endometriosis studies that have screen failure rates less than 10%, but given the nature of this study with daily compliance requirements, we anticipate the screening failure rate to be higher. Based on these estimates, we would anticipate screening roughly 70 patients to enroll our target number.

8.2 Sample size determination

We have chosen to enroll 36 participants. We have chosen this number based on the 2005 paper on pharmaceutic statistics by Julious et al., which states that 12 participants in a pilot study maximizes the balance between feasibility and precision.¹⁵

Given that this is a pilot study, we will not be using a power calculation to determine sample size. Information from this study will be used to determine the appropriate sample size to power further investigation.

8.3 Statistical methods

The statistical methods will primarily be descriptive given the sample size and intent of the study.

The primary study endpoint of daily pain (as measured using VAS) will be compared between groups using the area under the curve over the course of the 8-week intervention period. Subsequently, the AUC VAS score data will be normalized per participant to an average AUC VAS score per week (i.e., 7 days) to account for participants that withdraw early from the study. It is well described that endometriosis pain has a cyclic and not a linear pattern. This makes the use of averages and means less useful for monitoring progression of pain. The area under the curve of plots of daily pain should capture endometriosis "flairs" and cyclic pain allowing more accurate comparison between study groups.

We will account for the use of rescue analgesics in the efficacy analysis of CBD and ERP. We will adjust the pain score for analgesic use during the intervention. We will take into account that ERP is often cyclical.

We will compare changes from baseline in secondary study endpoints such as quality of life (QOL) and sexual function as assessed via validated surveys and inflammatory cytokines. We will compare these findings across treatment arms.

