3.0 Inclusion & Exclusion Criteria

3.1 Inclusion Criteria

1. Females ages 18-45 years at the time of enrollment

2. A surgical diagnosis with direct visualization and/or histopathologic confirmation of endometriosis with associated moderate to severe endometriosis related pain (> 3 on a VAS)

3. Is not expected to undergo gynecological surgery or other surgical procedure for treatment of endometriosis during the study period

4. Agrees to use approved contraception method during the entire study

5. Patients using oral contraceptives, vaginal ring, injectable progesterone and/or GnRH agonists/antagonist for contraception and/or management of endometriosis, can be included if both they and their primary provider agree to stopping their medication and transitioning to Norethindrone acetate (NETA) as the primary treatment of endometriosis throughout the study period.

6. Patients using a progesterone containing IUD or a copper IUD for contraception and/or management of endometriosis can be included if both they and their primary provider agree to initiate Norethindrone (NETA) as the primary treatment of endometriosis throughout the study period

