7.0 Study Design and Procedures

7.1 Study Design

We propose to conduct a randomized double–blind placebo-controlled pilot study to evaluate the effectiveness of cannabidiol on the management of endometriosis-related pain.

Potential subjects will be pre-screened in the Penn State Minimally Invasive GYN Surgery Clinic for moderate to severe endometriosis associated pain (VAS > 3). Subjects will be pre-screened from new and existing patients receiving care from the MIGs division of OBGYN for the diagnosis of endometriosis. Those meeting all inclusion and exclusion criteria who are willing to participate will receive a detailed history and physical exam, appropriate bloodwork and undergo informed consented at the Screening Visit. Baseline survey data will be collected and entered into the RedCap secured database. At this time,

Page 14 of 37 (V.01/21/2019)

subjects will be set up to receive automated links via email to complete daily diary entries (including VAS scores) directly into RedCap.

After the screening visit, the subjects will be scheduled to have a 1-2 week follow-up for the enrollment visit. During that week, the patient's will be asked to complete their daily electronic diaries and screened for daily reporting adherence. Subjects having completed 5 or fewer daily diary entries during this baseline collection period will be informed of the exclusion from enrollment without at least 80% adherence to the daily diary entries and offered one additional 7-day period to improve adherence. If at the conclusion of the second 7 day run in period of gathering baseline daily diary entries, they continue to have < 80% adherence, they will be considered a screen failure and withdrawn from the study.

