7.2.2 Study Visit 1: Screening Visit

Pre-screening will take place in the Penn State Hershey MIGS clinic or over the phone with women identified as potential candidates for study participation via prior clinic visits. If the subject meets all pre-screening criteria, she will return for a screening encounter and undergo informed consent prior to any study procedure. The subject will be given ample time to ask questions or voice concerns about the study.

A detailed history and physical exam will be performed, particularly to assess for concomitant use of anti-epileptic drugs and or underlying risk of liver dysfunction. We will need approximately 8-10 cc of blood (approximately 2 teaspoons).

- 1. Liver function tests (LFTs) will be drawn.
- 2. Baseline CBC and BMP will be drawn.
- 3. Screening urine toxicology will also be performed to confirm no recent THC use.
- 4. Urine pregnancy test will be collected.
- 5. Pain medication and narcotic usage from the prior month will be assessed.
- 6. Suicidal ideation will be assessed via the Columbia-Suicide Severity Rating Scale (C-SSRS).

If the subject is found to be pregnant, have evidence of underlying hematologic/ urologic/ hepatobiliary dysfunction or a positive urine toxicology for recent THC use, the subject will be excluded.

Current medication usage will be reviewed thoroughly with special attention paid to Cytochrome P450 (CYP) inducers and inhibitors as well as Substrates of uridine 5'-diphosphoglucuronosyltransferase (UGT). If the subject is screened into the study, their condition and corresponding medication will be recorded throughout the study. Please refer to Section 10 Risks, Drug Interactions, for additional guidelines.

Baseline survey data will be collected and entered into the RedCap secured database. This information will include the WERF EPHect Questionnaire.

At this time subjects will be set up for emails to complete VAS scores directly into RedCap. If not done already, the subject will be transitioned to norethindrone acetate to start taking immediately and given instruction on how to complete the VAS scores and study questions. It will be explained to the patient that she must complete 5 out of 7 days of surveys to be enrolled into the study. If the subject is unable to complete the 5 out of 7 days, the subject will be given one additional week to determine if compliance is attainable. If the subject is unable to do so, they will screen fail.

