7.2.3 Study Visit 2 – Enrollment Visit

The subject will be scheduled for a randomization/enrollment 1-2 weeks after the screening visit. The randomization will be double blind and 1:1:1. The patient will have been expected to be on norethindrone acetate (NETA) for 30 days prior to the enrollment visit. Dosing for norethindrone acetate will start at 5mg oral daily, but may be adjusted from 2.5 mg to 15 mg depending on the subject's needs to achieve amenorrhea as this standard treatment for endometriosis or to increase compliance by reducing side effects. The study team will be responsible for adjusting dosages at subsequent study visits 3 and 4. At this visit, the subject will be randomized into Group A, Group B, Group C by IDS as long as the subject has met all the criteria for enrollment. The groups are listed below:

Group	Treatment
А	Norethindrone acetate + Placebo (Hemp Seed Oil)
В	Norethindrone acetate + low dose CBD (10mg sublingual daily)
С	Norethindrone acetate + high dose CBD (20mg sublingual daily)

The subject will be given a 4 week supply of (1) placebo (2) low dose CBD or (3) high dose CBD product and instructed on its application. The subject will also receive a 4 week supply of norethindrone. Refer to the following:

- a. In the morning, take the norethindrone acetate orally with a sip of water at approximately the same time each day. This can be taken on an empty or full stomach.
- b. Prior to bed, you will administer the study drug.
 - 1. Please refrain from eating (drinking is permissible) 60 minutes prior to administration.
 - 2. Place 4 drops of the study drug under your tongue.
 - 3. Hold the study drug under the tongue for 60 seconds. After that time, swallow any remaining drug.
 - 4. Repeat steps 2 and 3 for a total of 8 drops.

Please avoid eating, drinking or smoking for 2 hours after administration.

A focus group was conducted to determine the optimal route of administration of the study drug. 1 application of 8 drops of the study drug versus 2 applications of 4 drops were compared and it was determined that the latter method was preferred.

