Subjects will be instructed to take ibuprofen as first line treatment and acetaminophen if additional pain relief is needed, both of which are available over the counter. Only if requested will a stronger medication be prescribed, such as oxycodone. If needed, the subject will be advised to take first the ibuprofen 600mg every 6 hours as needed for pain with food, then acetaminophen 500-1000mg every 8 hours as needed for pain. For breakthrough pain, patients will need to contact the study team and they will be given a prescription for oxycodone 5mg oral every 6 hours as needed. As the pain associated with endometriosis tends to be cyclical, even if

the patient reports the pain as mild at the enrollment visit, they may suffer from an endometriosis flare requiring short term opioid use. Refill prescriptions for opioid pain medications will be provided beyond the screening visit on an as needed basis and will not be routinely provided at any subsequent study visits unless there is a documented need.

At the enrollment visit, baseline study surveys and VAS scores will be collected and entered into the RedCap secured database. The will have inflammatory markers drawn at this visit (1 teaspoon, <5cc of blood)

Daily Diaries:

The subjects will be instructed as to how to complete their daily diaries directly into REDCap. They will enter daily VAS scores. They will be assessed as to their adherence of the study drug. We will document the daily use of any rescue analgesic medications and menstrual pattern.

Physical Assessment

A physical assessment will be performed at visits #2-5, following the detailed history and physical examination performed at the screening visit. This assessment will include, but is not limited to:

- 1. Vitals signs (blood pressure, pulse, O2; orthostatic assessment to be done only as indicated)
- Detailed, but directed review of systems that will include symptoms concerning for liver disease, stroke, new/worsening migraine, deep venous thrombosis (DVT), pulmonary embolism (PE). This review of systems will include an assessment of (new onset) visual abnormalities.
- 3. Directed physical exam as indicated from the ROS, including an examination of the oral cavity to assess for lesions/sores
- 4. Adverse event assessment. Please refer to Section 3.3.1
- 5. Review of concomitant medications

Patient Education:

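### Section 8.3 names no baseline term for the primary VAS AUC, although every woman randomised per protocol has at least five run-in daily VAS scores; adding one costs almost nothing and can narrow the intervals

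*Combined protocol and SAP*

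**What the plan says.** **Primary analysis.** Section 8.3 states that daily VAS pain "will be compared between groups using the area under the curve over the course of the 8-week intervention period", with each woman's AUC then rescaled to a weekly average. The one adjustment it names is for rescue medication: "We will adjust the pain score for analgesic use during the intervention". It adds that the cyclic nature of the pain will be considered, but specifies no term for this. Section 1.2 defines the endpoint as a between-group difference in daily VAS and does not mention baseline. Change from baseline appears in Section 8.3 only for the secondary endpoints.

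**Baseline data.** Section 7.1 sets up the daily diary, with VAS, at the screening visit and makes adherence a condition of enrolment. It is explicit about who falls short: "Subjects having completed 5 or fewer daily diary entries during this baseline collection period" are told they will be excluded "without at least 80% adherence to the daily diary entries and offered one additional 7-day period to improve adherence". A second shortfall is a screen failure. Section 7.2.2 sets a different minimum: "she must complete 5 out of 7 days of surveys to be enrolled into the study". Section 7.2.3 adds a further collection: "At the enrollment visit, baseline study surveys and VAS scores will be collected and entered into the RedCap secured database".

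**Size and purpose.** Sections 7.2.3 and 8.1 give 36 women randomised 1:1:1. Section 8.2 justifies the number by feasibility and precision, without a power calculation, and says the results will be used to size later work. Section 8.3 calls the methods primarily descriptive.

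**The concern.** The plan collects a week of daily pre-treatment pain scores from every woman it randomises, and accepts an expected 50% screen failure rate partly because of that daily burden. It then gives those scores no stated role in the primary comparison, although it uses baseline for quality of life, sexual function and cytokines.

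What is at stake is precision. With 12 women per arm the intervals are wide, and part of the spread in 8-week pain is the spread in pain that the women brought with them. Section 7.4.3 describes no stratification. Under simple randomisation, the chance difference in mean baseline pain between two arms therefore has a standard deviation of √(2/12) = 0.41 baseline SDs. A baseline term removes the part of that noise which carries through to the outcome. Precision is also the criterion that Section 8.2 uses to justify the sample size.

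The two run-in rules raise a separate question: whether a woman with exactly five entries is eligible. The answer also fixes the minimum number of scores behind the covariate.

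**Working it through.** **Inputs from the documents.** Three arms, 36 women, 1:1:1, hence 12 per arm.

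**Assumed, because the documents give no value.** A 95% interval, and r, the within-arm correlation between mean run-in VAS and the 8-week AUC, taken from 0 to 0.7. Half-widths are in SDs of the AUC, since no SD is stated.

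**The plan's own figures.** 3 × 12 = 36 reproduces. Screening at 50% failure needs 36/(1 − 0.5) = 72, against the stated figure of roughly 70.

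**Run-in minimum.** 80% of 7 is 5.6, so Section 7.1 requires six entries (6/7 = 86%). Section 7.2.2 accepts five (5/7 = 71%). A woman with five entries passes one rule and fails the other. Under either rule there are at least five scores.

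**Without baseline.** Residual df = 36 − 3 = 33. Half-width = t(0.975, 33) × √(2/12) = 2.0345 × 0.4082 = 0.831 SD.

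**With baseline as a covariate.** Residual df = 32. Half-width = t(0.975, 32) × √[(2/12)(1 − r²)(1 + 1/31)], where 1 + 1/31 is the expected cost of chance imbalance in the covariate. At r = 0 this is 2.0369 × 0.4082 × 1.0160 = 0.845 SD.

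| r | Half-width (SD) | Against 0.831 |
|---|---|---|
| 0 | 0.845 | 1.7% wider |
| 0.3 | 0.806 | 3% narrower |
| 0.4 | 0.774 | 7% narrower |
| 0.5 | 0.732 | 12% narrower |
| 0.7 | 0.603 | 27% narrower |

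The two widths are equal when 1 − r² = (0.8306/0.8449)², that is at r = 0.183. The gain at r = 0.5 is worth about 15.5 unadjusted women per arm, and at r = 0.7 about 23. In a simulation of 5,000 trials at each of r = 0, 0.3, 0.5 and 0.7, the ratios of mean half-widths were 1.017, 0.971, 0.882 and 0.728. The formula gives 1.017, 0.970, 0.881 and 0.726.

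**With the planned rescue adjustment.** Section 8.3 does not state the method.
- If the pain score itself is adjusted, the table holds in SDs of the adjusted AUC, with r defined on that AUC.
- If rescue use is one covariate in both models, unrelated to arm, the half-width without baseline is t(0.975, 32) × √[(2/12)(1 + 1/31)] = 0.845 residual SD. With baseline it is t(0.975, 31) × √[(2/12)(1 − r²)(1 + 2/30)], with r now the partial correlation. This gives 0.860, 0.820, 0.745 and 0.614 at r = 0, 0.3, 0.5 and 0.7: 1.8% wider, then 3%, 12% and 27% narrower. Break-even is 0.186.

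**Restricted range from the VAS > 3 entry rule.** As a stringent case, suppose the rule cut directly on the run-in mean and removed the lowest 10%, 25% or 50% of a normal distribution. The remaining variance fraction u² is 0.712, 0.535 or 0.363, and r becomes r·u/√(1 − r² + r²u²).
- r = 0.5 becomes 0.44, 0.39 or 0.33: half-width 0.76, 0.78 or 0.80 SD, which is 9%, 6% or 4% narrower.
- r = 0.3 becomes 0.26, 0.22 or 0.19: 2%, 1% or 0% narrower.

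**A change score is not equivalent.** With equal SDs at baseline and outcome, its width relative to no adjustment is √(2 − 2r): 18% wider at r = 0.3 and no gain at r = 0.5.

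**The case against.** The best case against acting is that this is a pilot with primarily descriptive methods and no power calculation. Section 8.3 names no model, test or interval, so the interval being narrowed is one the plan has not promised. Silence is also not exclusion. And because the diary data will exist, r and the residual SD can be computed later, so the next trial loses nothing permanently. All of this is correct. It limits the point to precision and keeps it well short of a fatal flaw. But the plan does compare groups on this endpoint, a descriptive difference is also more useful with less noise, and writing the term in now prevents it being chosen after the results are seen.

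A second objection is that r may be low. Seven days may catch or miss a flare. The entry rule restricts the range. Norethindrone acetate dosing can change during treatment: "The study team will be responsible for adjusting dosages at subsequent study visits 3 and 4". Section 7.2.2 also has some women start it at screening, just as the run-in diary begins, while Sections 7.2.1 and 7.2.3 expect 30 days on it before enrolment; those passages need reconciling. These factors move r within the range shown. They do not change the asymmetry between a loss of 1.7% and a possible gain of 12% or more.

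Third, withdrawn women are not replaced. If only nine per arm contributed, the cost at r = 0 would be about 2.5% and break-even about 0.22. That is still small.

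Finally, rescue use is measured after randomisation and may respond to treatment. That is a question about the plan's own adjustment, and adding baseline neither creates nor cures it.

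**Conclusion.** The point holds. Section 8.3 gives the primary VAS AUC no baseline term, and the required run-in diary supplies at least five daily scores for every woman randomised per protocol. Including their mean changes the pairwise 95% half-width from 0.83 SD to between 0.845 SD (r = 0) and 0.60 SD (r = 0.7). It helps whenever r exceeds about 0.18.

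These figures rest on 12 analysable women per arm, a linear relation with equal variances, and an assumed r; the documents do not settle where in the range the trial lies. No bias, invalid test or lasting harm to the next trial is claimed. The change is recommended as a better use of data already collected. The conflict between Sections 7.1 and 7.2.2 is real and stands independently of the value of r.

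**What to change.** In Section 8.3:

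- Analyse the weekly-normalised AUC in one linear model across the three arms, with mean run-in daily VAS as a covariate alongside the planned rescue-analgesic adjustment. Use a covariate, not a change score.
- Define the covariate as the mean of the available entries in the last 7-day run-in period before randomisation, meaning the period on which the woman qualified. State whether those scores receive any analgesic adjustment.
- Report arm differences with 95% intervals, baseline VAS by arm, r, and the residual SD for sizing the next trial.
- For the secondary endpoints, state whether the baseline value is a covariate as well as the reference for change.

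Reconcile Sections 7.1 and 7.2.2 on the minimum number of run-in entries.

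The cost is a few sentences and one degree of freedom, an expected 1.7% in interval width if baseline turns out to be uninformative. No new data, visits or participants are needed.

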1.0 Objectives

1.1 Study Objectives

Our central hypothesis is that Cannabidiol will result in a significant improvement of endometriosisrelated pain. This proposal seeks to (1) determine if cannabidiol will result in an overall improvement of patient-reported endometriosis associated pain (2) determine if this pain reduction is dose-dependent (3) determine if cannabidiol will result in improved sexual function (4) determine if cannabidiol will result in an overall improved quality of life among women with endometriosis (5) determine if CBD affects common inflammatory markers associated with endometriosis (6) to determine the pharmacokinetics of sublingual CBD. We propose a randomized double-blind placebo-controlled pilot study to achieve the following aims:

Aim 1: Identify the overall impact of cannabidiol (CBD) on endometriosis related pain. We plan to measure endometriosis related pain using daily self-reported Visual Analogue Scale (VAS) scores over an 8 week period.

Aim 2: Identify the dose-dependent impact of cannabidiol on endometriosis related pain. We will be dividing our patients into 3 arms – high dose CBD, low dose CBD and placebo. We plan to measure and compare endometriosis related pain using daily self-reported Visual Analogue Scale (VAS) scores.

Aim 3: Identify the overall impact of cannabidiol (CBD) on sexual function. This will be assessed via the Female Sexual Function Index (FSFI), a validated survey, to be administered to participants with current sexual partners that are sexually active.

Aim 4: Identify the impact of cannabidiol on Quality of Life (QOL) among women with endometriosis. We plan to measure QOL using the Endometriosis Health Profile-30 (EHP30), Patient Global Assessments (PGAs), and Patient Global Impression of Change (PGIC) surveys. These are validated health surveys.

Aim 5: To measure inflammatory cytokines that have been linked to the pathogenesis of endometriosis and to determine if CBD will alter these inflammatory markers.

Aim 6: On a small subset of patients (4), we will study the pharmacokinetics of sublingual CBD.

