Randomized subjects will receive either (1) placebo (2) low dose CBD (3) high dose CBD. This study will include an 8-week intervention period during which subjects will be asked to record daily electronic VAS scores, pain medication use and a number of other parameters. They will return at week 12 for a 4 - week post-treatment visit, where they can also choose to enroll in an optional pharmacokinetic study. Participants will complete the Endometriosis Health Profile-30 (EHP-30), Patient Global Assessments (PGAs), and, if partnered and sexually active, the Female Sexual Function Index (FSFI) surveys at 0, 4 and 8, 12 weeks as well as the Patient Global Impression of Change (PGIC) surveys at 4, 8, and 12 weeks. Patients will also have bloodwork done at weeks 0, 4, 8, 12 to assess for circulating markers of inflammation. At week 8, this bloodwork will include circulating CBD levels to assess for steady state concentrations. We will perform bloodwork to assess for possible side effects e.g. liver dysfunction throughout the study duration. Please refer to Section 7.2 Study Procedures for timing and test.

Subjects will be screened for side effects and asked to record pain medication use throughout the duration of the study. At each visit, subjects will be dispensed a 4 week supply of medication **(NETA and CBD)** from the Investigational Pharmacy. They will be required to bring medication bottles to each visit to verify drug accountability. Oxycodone (if prescribed) and NETA pills will be counted and recorded. Additional refills will be provided as needed. The study drug bottle will be inspected and returned to the clinician. The patient will be provided with a new supply of study drug at Visit 3. All NETA and study drug will be returned at the completion of the study.

At the completion of the study, all subjects will be offered the opportunity to do pharmacokinetic testing with sublingual CBD until a maximum number of 4 patients are enrolled. We plan for a total of 3-4 patients. This will be entirely voluntary and they will be compensated appropriately for their time. The testing will include 24 hours of monitoring with sequential blood draws to determine the pharmacokinetic parameters of sublingual CBD after administration and one salivary pH. They will be discharged at 24 hours and asked to return to the clinic at 48 hours for one final lab draw. We will stop recruitment once we have achieved the desired number of participants.

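### Section 8.3 compares secondary endpoints only by change from baseline, which is less precise than adjusting for week 0 and cannot be applied to PGIC

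*Combined protocol and SAP*

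**What the plan says.** Section 8.3 gives one method for the secondary endpoints: "We will compare changes from baseline in secondary study endpoints such as quality of life (QOL) and sexual function", with inflammatory cytokines named in the same sentence. It adds: "We will compare these findings across treatment arms". It does not say whether change is absolute, percentage or logarithmic, whether the week-0 value enters a model, or which visit is the main one. The section opens with: "The statistical methods will primarily be descriptive given the sample size and intent of the study".

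Aim 4 in Section 1.1 defines quality of life by three instruments: "We plan to measure QOL using the Endometriosis Health Profile-30 (EHP30), Patient Global Assessments (PGAs), and Patient Global Impression of Change (PGIC) surveys". Section 1.3 also lists PGIC under the quality-of-life endpoint.

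Section 7.1 sets the visits. EHP-30 and PGA share the schedule of the sexual function survey: "if partnered and sexually active, the Female Sexual Function Index (FSFI) surveys at 0, 4 and 8, 12 weeks". Cytokines are also sampled from week 0: "Patients will also have bloodwork done at weeks 0, 4, 8, 12 to assess for circulating markers of inflammation". PGIC starts later: "as well as the Patient Global Impression of Change (PGIC) surveys at 4, 8, and 12 weeks". The procedures table in Section 7.2 and the visit descriptions in Sections 7.2.4 to 7.2.6 agree with this.

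**The concern.** Aims 3, 4 and 5 rest on this one sentence. Two things follow from it.

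First, a plain change score subtracts the whole week-0 value, including its noise. When week 0 and follow-up are imperfectly correlated, that subtracts too much: an arm that starts worse by chance tends to show a larger apparent improvement. Arms of 12 leave room for sizeable chance differences at week 0. FSFI is completed only by partnered, sexually active women, so its arms may be smaller still.

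Second, PGIC falls under the quality-of-life rule but has no week-0 value to subtract. Read literally, the plan leaves one of the three Aim 4 instruments without a workable analysis.

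The descriptive label does not remove the first issue, because a described difference in mean change carries the same imbalance and the same extra variance as a tested one. Section 8.2 says that the results will be used to size later work, so imprecise estimates would pass into that planning.

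**Working it through.** **Inputs from the documents.** 36 women in total (Section 8.2); 1:1:1 allocation to three arms (Section 7.2.3); 12 per group, from the title of the reference cited in Section 8.2. Check: 12 × 3 = 36, which reproduces the plan's figure.

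**Assumed inputs.** The documents give no correlation (rho) between week 0 and follow-up, so a range of 0.3 to 0.8 is used. Variances at the two visits are taken as equal, and results are in units of that common SD.

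**Precision.** With n = 12 per arm, the standard error (SE) of a pairwise contrast is sqrt(2V/n), where:

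- plain change: V = 2(1 − rho)
- adjusted for week 0: V = (1 − rho²) × (1 + 1/31)

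The factor 1 + 1/31 is the cost of estimating one slope pooled over three arms: 3 × (12 − 1) = 33 within-arm degrees of freedom, and 33 − 2 = 31. The number per arm that plain change needs to match 12 adjusted is 12 × V(change) / V(adjusted).

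| rho (assumed) | SE, plain change | SE, adjusted | Plain-change n per arm to match | Excess |
|---|---|---|---|---|
| 0.3 | 0.483 | 0.396 | 17.9 | 49% |
| 0.5 | 0.408 | 0.359 | 15.5 | 29% |
| 0.7 | 0.316 | 0.296 | 13.7 | 14% |
| 0.8 | 0.258 | 0.249 | 12.9 | 8% |

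Worked line for rho = 0.5: V(change) = 1.0 and V(adjusted) = 0.75 × 32/31 = 0.774, so 12 × 1.0/0.774 = 15.5.

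**Chance imbalance.** The week-0 difference between two arms of 12 has SD sqrt(2/12) = 0.41, and a 22% chance of exceeding 0.5 SD in either direction. Given a week-0 difference d, the plain-change contrast is shifted by −(1 − rho)d. For d = 0.41 the shift is 0.29, 0.20, 0.12 and 0.08 SD at rho 0.3, 0.5, 0.7 and 0.8. Averaged over randomizations it is zero. The shift is already part of the plain-change SE in the table and is not an additional loss.

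**PGIC.** The rule needs a week-0 value; the scheduled visits are weeks 4, 8 and 12. There is nothing to subtract.

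**Cytokines.** The documents give neither a distribution nor a scale, so the following only illustrates why the scale should be fixed in advance. Simulation assuming lognormal values: two arms of 12, 40,000 runs, rho 0.5, a 50% reduction in one arm, tests at 5%.

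| CV (assumed) | Power, raw change | Power, log change | Power, log scale adjusted for week 0 |
|---|---|---|---|
| 0.53 | 0.67 | 0.90 | 0.95 |
| 1.0 | 0.26 | 0.50 | 0.59 |
| 1.31 | 0.17 | 0.37 | 0.45 |

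With no true effect, rejection rates stayed at about 0.05 or below. Under this assumption, raw change costs sensitivity and does not add false positives.

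**The case against.** The strongest defence is that this is a thin specification in a small, mainly descriptive pilot. No test, alpha or power calculation attaches to these endpoints. Section 8.3 does not exclude a baseline covariate, and change can be modelled with one. PGIC is itself a rating of change, and Section 1.3 states the quality-of-life endpoint as a difference between groups, which PGIC fits directly. At rho 0.7 to 0.8 the gain in SE is small. Much of this stands: it limits the consequence and makes the PGIC point minor. It does not supply the missing analysis, and leaving the covariate open means that the choice could be made after the data are seen.

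A reader might also infer stronger points that the documents do not support:

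- **That the rule covers every secondary endpoint.** The sentence gives examples and does not name pharmacokinetics, which Section 1.3 also lists as secondary.
- **That the cytokines will be analysed on the wrong scale.** No scale or distribution is stated, and a log or percentage change is also a change from baseline. Only an unspecified scale can be shown.
- **That change scores bias the trial.** The shift is conditional on the imbalance that occurs and is zero on average over randomizations.
- **That the penalty is 54%, 33% and 18%.** These follow from the large-sample variance ratio (1 + rho)/2 and omit the cost of estimating the slope.

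**Conclusion.** The point holds as one of precision and incomplete specification. For EHP-30, PGA and FSFI, adjusting for the week-0 value is a better method than the plain change that the plan states. At 12 per arm the gain equals about 49%, 29% and 14% more women at rho 0.3, 0.5 and 0.7, falling to 8% at 0.8. These figures assume the correlation, equal variances at the two visits and full arms of 12. FSFI arms may be smaller, which would make chance imbalance larger.

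For PGIC, the rule cannot be applied as written. This follows from the documents alone, but it is easily settled because the rating already expresses change. For cytokines, the supported conclusion is only that the scale is not stated.

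None of this touches the primary AUC analysis or the sample size of 36. It is a free or cheap improvement.

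**What to change.** Replace the secondary-endpoint sentences in Section 8.3 with wording to this effect:

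- **EHP-30, PGA and FSFI:** estimate differences between arms, with 95% confidence intervals, from a linear model with arm and the week-0 value. Week 8 is the main time point; weeks 4 and 12 are also reported.
- **PGIC:** summarise by arm as its own rating at weeks 4, 8 and 12, with no baseline.
- **Cytokines:** adjust for the week-0 value at each scheduled visit. State the scale in advance (log scale if skewed, which is an assumption here) and give a rule for undetectable values.

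Keeping all visits matters. Section 1.3 asks for cytokine levels during treatment as well as before it and at its end, so a week-8-only analysis would drop part of the endpoint.

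The cost is protocol wording and one degree of freedom per model. No visit, sample or participant is added, since every week-0 value used is already scheduled. A rule is needed for a missing week-0 value, for example a woman with no FSFI at enrollment; plain change needs the same rule.
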